Eligibility criteria: Individuals aged over 18 years as of January 2008, with medical conditions that indicate corticosteroid therapy (listed below) who have not had corticoid prescriptions dispensed in the preceding 6 months. Patients receiving palliative care, those

presenting with malignancy-related symptoms, medical complications or those receiving treatment post-organ transplantation will be excluded to void confounding effects.

Treatment strategies Eligible patients will be randomized into two treatment groups. One group will receive methylprednisolone tablets, while a second group will receive prednisolone tablets. The dosages for both methylprednisolone and prednisolone will be determined at the discretion of the treating physician, customized for the specific clinical need in accordance with local guidelines.

Treatment assignment The treatment strategy will be randomly assigned at baseline. Patients will be aware of which drug they have been assigned.

Outcomes The primary outcome is acute decompensated heart failure leading to acute contact with secondary or tertiary healthcare facilities during the first 6 months after treatment initiation. Secondary outcomes include the initiation or escalation of loop diuretics. A composite of both primary and secondary outcomes will also be assessed.

Follow-up Participants will be followed from the baseline until the occurrence of the primary outcome, death, emigration, loss to follow-up, or at 6 months post-baseline, whichever occurs first.

Statistical analysis The primary comparative analysis between the two treatment groups will be performed on an intention-to-treat basis, with all randomized patients in their initially assigned groups. For the primary outcome, survival plots with restricted mean survival time (RMST) differences with 95% confidence intervals will be applied to estimate the treatment effect size. Secondary outcomes will be analyzed using the appropriate statistical tests based on their distribution. Missing data will be handled appropriately using multiple imputation methods. All analyses will be two-sided, with a significance level set at 0.05.

4. Data sources for target trial emulation

This registry-based study will include data from the nationwide Norwegian Cardio-Rheuma Registry (NCRR) that encompasses the entire Norwegian adult population over a ten-year period from January 2008 to December 2017.

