The registry is approved by the Norwegian General Data Protection Regulation (16/00482-11/CDG), the South East Norway Health Authority Ethical Committee (2016/588), and the Data Protection Officers at Oslo University Hospital (2016/924) and Diakonhjemmet Hospital (7/12–2019). The NCRR comprises routinely recorded administrative data, and written consent from study subjects was not required.

For this study, we will use data from three key sources: The Norwegian Prescription Registry (NPD) serves as the foundation for prescription data, The Norwegian Patient Registry (NPR) provides diagnosis data, and data regarding age and sex are extracted from Statistics Norway (SSB). The data from these registers provide accuracy up to the month and year, but not to the exact date of events, like prescriptions or diagnoses.

5. Data preparation and eligible treatment periods in the target trial emulation

To maintain comparability between the methylprednisolone and prednisolone treatment groups in the emulated study, we will apply several data management steps:

- 1) Individuals aged \leq 18 years in January 2008 will be excluded
- 2) Analyses will be restricted to tablets, as prednisolone is only available in this form.
- 3) To allow for equipotent dose comparisons, we will focus only on 4 mg and 16 mg methylprednisolone and their counterparts in prednisolone at 5 mg and 20 mg, respectively. Patients with other doses will be excluded.
- 4) To facilitate comparisons of treatments prescribed for similar conditions, we will only include prescriptions with an International Classification of Diseases, 10th Edition (ICD10) or International Classification of Primary Care, 2nd Edition (ICPC2) refund code.
- 5) Patients with prescriptions for diagnosis codes including palliative care, cancer symptoms, medical complications, and organ transplants will be excluded. This exclusion aims to reduce the inherent heterogeneity within these groups, allowing for a more comparable baseline risk.
- 6) An initial 2-year observational period, spanning from January 2008 to December 2009, will be used to establish comorbidities. Accordingly, only prescriptions of methylprednisolone or prednisolone dispensed from January 2010, onward, will be eligible for analyses.

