- 7) To minimize the risk of carry-over effects, we will exclude all prescriptions prescribed \leq 6 months after another prescription for a corticosteroid. Accordingly, the same patient can contribute data on several treatment courses, provided that there was $>$ 6 months since the last prescription was dispensed (See section 7 for justification for why a 6-month interval was chosen).
- 8) Duplicate prescriptions (same date, drug and dosage) will be kept in the analyses as a single treatment course. Cases of duplicate prescriptions on the same date, but where the drug or dosage is different will be excluded.

9) Baseline of the treatment course will be defined as the date when the prescription of either methylprednisolone or prednisolone was dispensed.

6. Emulated target trial matching procedure

In order to create balanced treatment groups and reduce the potential for confounding in the emulated study, we will apply a matching process for baseline characteristics including relevant comorbidities. Each methylprednisolone treatment course will be matched 1:1 with a prednisolone treatment course. The following characteristics will be matched for:

- Sex
- Age groups, defined as: < 45 years; 45 up to < 60 years; 60 up to < 75 years; 75 years or higher
- Equipotent dosage (4 mg methylprednisolone versus 5 mg prednisolone; 16 mg methylprednisolone versus 20 mg prednisolone). While prescription data from the NPD cannot provide the exact number of tablets of either medicine taken per day, we will assume that since the medications are taken by comparable populations and for comparable conditions, any differences will even out in this large dataset.
- Prescription groups based on ICD10 / ICPC2 refund codes:
 - i. Pulmonary
 - ii. Rheumatology and musculoskeletal
 - iii. Neurology and ophthalmology
 - iv. Dermatology
 - v. Endocrinology and metabolic
 - vi. Gastrointestinal
 - vii. Hematology and immunology
 - viii. Nephrology.
- Comorbidities as categorical variables (a. – e. defined as at least one ICD10 diagnosis code from a secondary or tertiary healthcare provider or at least one prescription of medication with relevant ICPC2 or ICD10 refund codes)
 - a. Atherosclerotic cardiovascular disease (coronary, cerebral and peripheral artery disease)
 - b. Chronic kidney disease
 - c. Diabetes (type 1 and 2)
 - d. Hypertension
 - e. Heart failure

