Our understanding of potential carry-over effects from one corticosteroid treatment course to another is limited. Thus, the ideal approach for our study would involve analyzing only the first instance of corticosteroid therapy to avoid such effects. However, since our dataset begins in January 2008, tracking the initial therapy instance for each patient is not

feasible. Given the findings of Souverein *et al.* that the cumulative corticosteroid dose was not associated with heart failure, and considering that the risk did not significantly increase between months 3 and 12 compared to after 12 months, we believe that a prescription dispensed ≥ 6 months after the last one provides a sufficient buffer. This approach ensures minimal residual effects from the previous treatment within the constraints of our dataset.

8. Primary outcome in the emulated target trial

The primary outcome of interest is an acute hospital contact (secondary or tertiary healthcare facilities) where the patient was given a primary diagnosis code for heart failure (ICD10 code i50*) at discharge. As discussed in section 7, the outcome will be assessed from the first day of the month after the corticosteroid prescription was dispensed and the following 5 months. This window will not be extended in cases where subsequent prescriptions for the corticosteroid is made so that the treatment course is longer than 6 months.

9. Secondary outcomes in the emulated target trial

Three secondary outcomes will complement the primary analysis. As for the primary outcome, we will investigate outcomes occurring during the first 6 months following the prescription of methylprednisolone or prednisolone. The secondary outcomes are as follows:

1. Any contact (acute or elective) with secondary or tertiary healthcare facilities where a primary diagnosis of heart failure is recorded
2. Initiation of newly prescribed loop diuretics or any increase in doses within the first 6 months after the prescription of methylprednisolone or prednisolone.
3. A combination of secondary outcome 1. and 2.

10. Subgroup analyses in the emulated target trial

The primary and secondary outcomes will be analyzed for the study population as a whole and within the following subgroups:

1. Only individuals with existing heart failure
2. Only individuals with existing heart failure or established ASCVD
3. Only individuals with at least 3 comorbidities (a. to g.)

11. Statistical analysis in the in the emulated target trial

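### Repeat courses are eligible, but prior corticosteroid use is not matched, not tabulated and not named for adjustment

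*SAP*

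**What the plan says.** Section 5 item 7 excludes a prescription dispensed up to "6 months after another prescription for a corticosteroid" and draws the consequence that "the same patient can contribute data on several treatment courses" once more than 6 months have passed. The rule covers any earlier corticosteroid, whichever drug it was.

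Section 6 sets the unit of matching: "Each methylprednisolone treatment course will be matched 1:1 with a prednisolone treatment course". The listed factors are sex, four age groups, equipotent dosage, eight prescription groups and seven comorbidity items (a to g). None concerns earlier corticosteroid courses, the time since the last one, or which drug it was.

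Section 11 summarises age, sex, comorbidities and refund codes at baseline. It leaves the outcome method open and names no adjustment covariate. Section 12 does not list imbalance in prior use among the limitations.

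Section 7 gives the reasoning. It states that "the ideal approach for our study would involve analyzing only the first instance of corticosteroid therapy to avoid such effects", finds this infeasible because the data begin in January 2008, and concludes that "a prescription dispensed ≥ 6 months after the last one provides a sufficient buffer". It offers two supports from the cited case-control study: no association with cumulative dose, and no significantly higher risk at 3 to 12 months than after 12 months.

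Section 5 item 6 states: "An initial 2-year observational period, spanning from January 2008 to December 2009, will be used to establish comorbidities". Courses become eligible only from January 2010.

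**The concern.** A washout limits how much of an earlier course can carry over into the next. It does not make the remaining history equal in the two arms. Under the plan, a course with no corticosteroid in the previous 24 months and a course just past the 6-month gap meet the same criterion and can form a pair. If the mix of such courses differs by drug, prior use and what goes with it (residual risk, chronicity of the treated disease) are confounded with treatment.

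The reason given for not restricting to first courses rules out identifying first-ever use. It does not rule out a fixed look-back, and the data for one are already held. Because prior use is also absent from the planned Table 1, an imbalance would not be visible to the reader.

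Direction matters for interpretation. Section 12 would treat a result favouring methylprednisolone as especially credible because the expected bias runs the other way. More prior users among the prednisolone courses would run in favour of methylprednisolone, and nothing in the plan would show whether this had happened.

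**Working it through.** The SAP gives no sample size, event count or share of repeat courses, so there is no design figure to reproduce. Three things can be checked: the look-back, the recency statement in Section 7, and the size of bias under assumed shares.

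**1. Look-back.** Data start in January 2008 and the earliest eligible course is January 2010. January 2008 to December 2009 is 24 months, so every eligible course has at least 24 months of earlier dispensing data.

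**2. The recency statement.** Inputs from Section 7: recent use (3 to 12 months) OR 1.40 [1.27 to 1.55]; past use (over 12 months) OR 1.19 [1.08 to 1.32].

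- SE of ln OR = (ln upper − ln lower)/(2 × 1.96). Recent: (ln 1.55 − ln 1.27)/3.92 = 0.0508. Past: (ln 1.32 − ln 1.08)/3.92 = 0.0512.
- Ratio = 1.40/1.19 = 1.18; ln = 0.1625.
- SE of the difference, if independent = √(0.0508² + 0.0512²) = 0.0721.
- z = 0.1625/0.0721 = 2.25; two-sided p = 0.024; 95% CI 1.02 to 1.36. Rounding of the two ORs moves p only between 0.018 and 0.032.
- A shared reference group would normally make the two estimates positively correlated, which strengthens the contrast: p = 0.009 at a correlation of 0.25 and 0.001 at 0.5. The difference is non-significant only if the correlation is below about −0.32.

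The two intervals do overlap (1.27 to 1.32), but overlap alone does not make a difference non-significant. The past-use interval also excludes 1.

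**3. Possible size of the bias.** Let p1 and p0 be the shares of courses with recent prior use in the two arms, and RR the risk ratio attached to it. The spurious ratio is [1 + p1(RR − 1)]/[1 + p0(RR − 1)]. The shares are assumptions, and ORs are used as risk ratios.

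*Recent against past use, RR = 1.40/1.19 (1.1765 unrounded):*
- 30% vs 20%: (1 + 0.3 × 0.1765)/(1 + 0.2 × 0.1765) = 1.0529/1.0353 = 1.02
- 50% vs 20%: 1.0882/1.0353 = 1.05

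*Three categories, recent 1.40, past 1.19, none 1.00 (assumed reference):*
- Comparison arm at 20/20/60%: 0.2 × 1.40 + 0.2 × 1.19 + 0.6 = 1.118
- Other arm at 30/20/50%: 0.420 + 0.238 + 0.500 = 1.158; ratio 1.158/1.118 = 1.04
- Other arm at 50/20/30%: 0.700 + 0.238 + 0.300 = 1.238; ratio 1.238/1.118 = 1.11

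If the imbalance is reversed, the last two become 1/1.04 = 0.97 and 1/1.11 = 0.90.

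**4. Cost of exact matching.** The current list defines 2 × 4 × 2 × 8 × 2⁷ = 16,384 cells. Adding prior use as none, or two recency bands by two last drugs (5 levels), gives 16,384 × 5 = 81,920.

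**The case against.** The SAP does not hide the issue. It names carry-over, states the ideal, explains why it cannot be reached, and argues for the gap partly on the absence of a cumulative-dose association. Section 11 does not forbid adjustment, and an E-value is planned for residual confounding. All of this stands. But the argument is about washout length, one of its two supports conflicts with its own figures, adjustment left open is not prespecified, and an E-value is a poor substitute for adjusting for something measured.

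The figures above are also only a guide. No arm shares are given. The 3 to 12 month category only partly overlaps gaps of more than 6 months. The cited ORs are set against current use in the SAP's account, whereas every course here starts current use, so carrying them over as multipliers is an assumption. A group with none in 24 months may still contain older users. These points stand and keep the estimate modest.

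Three stronger readings are tempting and are not supported:

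- *The plan fails to emulate a trial of new starters.* The target trial in Section 3 admits patients "who have not had corticoid prescriptions dispensed in the preceding 6 months", so it allows older use under the same 6-month criterion.
- *Switching after heart failure on the other drug adds to the bias.* A switch within 6 months is excluded by item 7 whichever drug came first, and heart failure is a matching factor (though the SAP does not say clearly whether comorbidity status is updated to baseline).
- *Methylprednisolone courses must have more prior use because prednisolone is the commoner drug.* That suggests prednisolone will often be the last drug in both arms. It says nothing about the amount or recency of prior use by arm.

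**Conclusion.** The point holds as a gap in control of a measurable confounder. Repeat courses are eligible, prior corticosteroid history is absent from matching, from Table 1 and from any named adjustment, and the look-back needed to handle it exists. Separately, the Section 7 statement on recency is not supported by the ORs cited in the same section (ratio 1.18, 95% CI about 1.02 to 1.36, p about 0.02 if independent).

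The likely effect is small: a spurious ratio of about 1.02 to 1.05 using recent against past use, and up to about 1.11 against an assumed no-use reference, or the inverse of these. This rests on assumed shares of 30 to 50% against 20% and on applying the cited ORs to patients starting a new course. The documents establish neither that an imbalance exists nor which way it would run. This is a low-cost improvement that should be made, not a flaw that invalidates the design.

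**What to change.** 1. Derive prior corticosteroid use over a common 24-month look-back for every course: none; last dispensed more than 12 to 24 months before; last dispensed more than 6 to 12 months before. Report it by arm in Table 1, together with the drug last dispensed.
2. Adjust for the prior-use category in the outcome model. Do not add it to the exact-matching cells: with recency and last drug these would rise from 16,384 to 81,920, and the loss of pairs cannot be judged because the SAP gives no sample size.
3. Prespecify a sensitivity analysis limited to each patient's first eligible course with no corticosteroid dispensed in the preceding 24 months, re-matched within that set.
4. Correct the Section 7 statement on recency so that it agrees with the ORs it cites. In the same edit, reconcile the gap wording: Section 5 requires more than 6 months, while Section 7 allows exactly 6.

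The cost is SAP wording, one derived variable (with the last drug for Table 1) from data already held, and lower precision in the sensitivity analysis.

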Corticosteroids have found widespread application in the treatment of numerous diseases, ranging from autoimmune disorders to allergic reactions. Although unified in purpose, corticosteroids differ significantly in their molecular structures and resultant effects. One defining characteristic is the balance between glucocorticoid and mineralocorticoid effects. It is primarily the glucocorticoid effects that clinicians seek when prescribing corticosteroids, owing to their pronounced anti-inflammatory and immunosuppressive properties. However, the mineralocorticoid effects are not without consequence, as they may result in sodium and fluid retention, as well as increased potassium excretion. The implications of these latter effects, particularly for patients with heart disease, have been a topic of discussion. Indeed, previous studies have reported an association between corticosteroid use and risk of heart failure decompensation (1–3). It has therefore been hypothesized that for patients with heart failure, corticosteroids with a diminished mineralocorticoid potency may be beneficial, though concrete clinical evidence remains elusive.

Prednisolone is the most frequently prescribed corticosteroid. Although methylprednisolone shares many of the therapeutic indications with prednisolone, a notable distinction between the two lies in their relative potencies: While methylprednisolone exhibits a superior glucocorticoid effect, its mineralocorticoid effects are considerably milder.

2. Objective

This Statistical Analysis Plan (SAP) outlines the methodology for an emulated target trial in a Norwegian health registry study aimed at comparing the effects of methylprednisolone and prednisolone on the risk of acute decompensated heart failure. We hypothesize that the differences in mineralocorticoid effects between the two medications will lead to lower rates of acute decompensated heart failure in patients treated with methylprednisolone compared to prednisolone. This SAP guides the statistical analysis by first detailing the target trial protocol and then the procedures that will be employed to emulate the target trial, including data handling, outcome assessment, and methodological approaches.

3. Protocol for target trial

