- Descriptive Statistics: The study will commence with descriptive statistics to provide an overview of baseline patient characteristics. This will include the calculation of means,

medians, standard deviations, and proportions to summarize key characteristics: Age, sex, comorbidities and glucocorticoid refund codes. Data will be presented in Table 1.

- *Primary and secondary outcomes*: We will employ appropriate statistical methods / survival analyses to assess the relationship between dichotomous treatment variables (methylprednisolone or prednisolone) and dichotomous outcomes of interest. These methods will be chosen based on the distribution and characteristics of the data, with consideration given to the matched nature of the study design and the requirements of each statistical test for valid results. Subgroup analyses will only be performed in the event of significant results in their respective primary and / or secondary outcome analyses. If manuscript formatting guidelines allow it, data will be presented in Figure 1 and 2. Sensitivity analyses including fatalities during follow-up will be presented in Figure 3.

- *E-value for sensitivity analyses*: To evaluate the robustness of our observed associations to potential unmeasured or residual confounding, we will calculate the E-value as described by VanderWeele and Ding (4).

- *Statistical Software*: The statistical analysis will be carried out using STATA MP16. A significance level of 0.05 will be used for all hypothesis tests.

12. Considerations about possible bias and limitations to the emulated target trial

Our emulated target trial will be subject to several sources of bias and potential limitations that merit consideration. First, the data we have is accurate only to the month and year, not to the exact date of events like prescriptions or diagnoses. This lack of precision can introduce temporal biases, particularly in the calculation of the duration between prescription dispensation and subsequent health outcomes. The imprecision in timing could either overestimate or underestimate the association between corticosteroid use and heart failure decompensation.

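### The subgroup plan specifies no analysis showing whether the drug difference depends on heart failure, and subgroup 2 can be significant on heart failure patients alone

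*SAP*

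**What the plan says.** Section 10 of the SAP introduces the subgroups with "The primary and secondary outcomes will be analyzed for the study population as a whole and within the following subgroups". The list is:

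- Subgroup 1 takes the patients who already have heart failure.
- Subgroup 2 widens this to "Only individuals with existing heart failure or established ASCVD".
- Subgroup 3 counts the seven matched comorbidities of section 6: "Only individuals with at least 3 comorbidities (a. to g".

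Section 11 sets the condition for running them: "Subgroup analyses will only be performed in the event of significant results in their respective primary and / or secondary outcome analyses". It leaves the method open ("We will employ appropriate statistical methods / survival analyses to assess the relationship between dichotomous treatment variables") and fixes the alpha: "A significance level of 0.05 will be used for all hypothesis tests". Neither section names an interaction term, a heterogeneity test or a complementary group.

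The Background gives the clinical motive: "It has therefore been hypothesized that for patients with heart failure, corticosteroids with a diminished mineralocorticoid potency may be beneficial". Section 6 makes heart failure, ASCVD and the other five comorbidities matching factors.

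**The concern.** Each subgroup is analysed on its own and only on the higher-risk side. Significance inside a subgroup does not measure effect modification. That needs an estimate in the complement and a comparison of the two. Because the motive for the study concerns heart failure, whether the drug difference depends on heart failure is the natural question for section 10, and no listed analysis addresses it.

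The containment of subgroup 1 in subgroup 2 adds a second difficulty. A positive subgroup 2 does not say whether patients with ASCVD but no heart failure benefit, because the heart failure patients may produce the whole signal.

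The significance condition in section 11 works in the other direction. If a benefit is confined to heart failure patients and diluted to non-significance in the whole population, the heart failure subgroup is never examined for that outcome.

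**Working it through.** The SAP gives no event counts, power or effect sizes, so there is no planned figure to reproduce. Step 1 uses the SAP's definitions only. Steps 2 to 5 are illustrations, and their event shares, effects, event counts and power are all assumptions.

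**Step 1: how the subgroups relate.** Seven yes/no comorbidities give 2^7 = 128 possible profiles. These counts show set relations, not patient proportions.

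| Set | Profiles |
|---|---|
| Subgroup 1 (heart failure) | 64 |
| Subgroup 2 (heart failure or ASCVD) | 96 |
| Subgroup 2 minus subgroup 1 (ASCVD without heart failure) | 96 − 64 = 32 |
| Subgroup 3 (at least three of seven) | 99 |
| In subgroup 3, not in subgroup 2 | 16 |
| In subgroup 1, not in subgroup 3 | 7 |
| In subgroup 2, not in subgroup 3 | 13 |
| In no subgroup | 16 |

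Subgroup 1 is contained in subgroup 2. Subgroup 3 contains neither and is contained in neither; it overlaps both.

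**Step 2: can subgroup 2 be positive on heart failure patients alone?** Let s be the share of subgroup 2's prednisolone-arm events that come from heart failure patients. Assume a true risk ratio of 0.70 with heart failure and 1.00 with ASCVD only. With 1:1 matching the pooled risk ratio is s × 0.70 + (1 − s) × 1.00.

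- s = 0.5: 0.35 + 0.50 = 0.85
- s = 0.7: 0.49 + 0.30 = 0.79
- s = 0.8: 0.56 + 0.20 = 0.76

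The same point on the hazard-ratio scale uses an assumed 400 events in subgroup 2, hazard ratios of 0.70 and 1.00, and variance 4/events, with matched-pair correlation ignored and no conditioning on the overall result. Here s is the share of all subgroup 2 events. The pooled log HR is s × ln 0.70, the expected z is s × 0.357 × √(400/4), and the probability of significance is Φ(z − 1.96).

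| s | Pooled HR | Expected z | P(subgroup 2 significant) |
|---|---|---|---|
| 0.5 | 0.84 | 1.78 | 43% |
| 0.7 | 0.78 | 2.50 | 70% |
| 0.9 | 0.73 | 3.21 | 89% |

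In every row the added ASCVD patients have no effect. Over 200 to 800 events and heart failure hazard ratios of 0.6 to 0.8, the probability runs from 12% to nearly 100%.

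**Step 3: what does significance in subgroup 1 mean after a significant overall result?** Assume the same effect everywhere and 80% overall power, so the overall z has mean 1.96 + 0.84 = 2.80. If heart failure carries a share w of the events, the subgroup z has mean 2.80 × √w and correlation √w with the overall z. The probability that the subgroup is significant, given that the whole population is, comes to:

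- w = 0.2: 28%
- w = 0.4: 51%
- w = 0.6: 70%

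There is no effect modification in this set-up, so the difference between 28% and 70% reflects event share only.

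**Step 4: dilution and the significance condition.** With the risk ratio of 0.70 confined to heart failure, and heart failure supplying 20% of the comparator-arm events in the whole population, the overall risk ratio is 0.2 × 0.70 + 0.8 × 1.00 = 0.94. If that result is not significant, section 11 stops the heart failure analysis for that outcome.

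**Step 5: precision of a contrast.** For heart failure yes versus no, the ratio of its standard error to the overall one is √(1/w + 1/(1 − w)).

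- w = 0.2: √(5 + 1.25) = 2.5
- w = 0.4: √(2.5 + 1.67) = 2.0

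The narrower contrast of heart failure versus ASCVD without heart failure, in the 400-event illustration, has standard error √(4/(400s) + 4/(400(1 − s))). Its power is 43%, 37% and 19% at s = 0.5, 0.7 and 0.9.

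**The case against.** The strongest reply is that the SAP never promises to test effect modification. Its own hypothesis in section 2 is a lower rate with methylprednisolone than with prednisolone, without restriction to heart failure. The Background sentence reports a hypothesis about heart failure patients and does not say that others would not benefit. Progressively higher-risk subsets can serve as a consistency check where absolute risk is larger. This stands in part: the SAP announces no unsupported subgroup claim. But it also sets no rule for reading the subgroups, and its motive invites the heart failure reading.

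A reader might infer that the plan makes the question unanswerable. The documents do not support that. The whole population is analysed too, so no-heart-failure results could be derived if event counts were reported by arm, and the open wording on methods does not exclude an interaction term. What stands is that none of this is specified, and a contrast chosen after the subgroup results are known would be post hoc.

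A reader might also infer that all three subgroups are nested. They are not, as step 1 shows.

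The significance condition does limit isolated positive subgroups when there is no effect at all. The 28% to 70% figures are already conditional on passing it, so the difficulty of interpretation remains after it.

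Low power of the contrast is a fair objection. It is a reason to report the contrast as an estimate with its interval; it does not make within-subgroup p-values a substitute.

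**Conclusion.** The point holds as a gap in specification and an improvement worth making. Subgroup 1 lies within subgroup 2, subgroup 3 overlaps both, and sections 10 and 11 specify no complement and no treatment-by-subgroup contrast. Followed as written, the plan gives only within-subgroup results at 0.05, and only after a significant overall result. These do not show whether the drug difference depends on heart failure, and a positive subgroup 2 would not show benefit in ASCVD without heart failure.

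The set relations follow directly from the SAP. The sizes do not: they illustrate the mechanism under assumed values and do not predict this study's results. The whole-population primary estimate is unaffected.

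**What to change.** Amend sections 10 and 11 as follows.

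- Keep the heart failure subgroup. Add, or put in place of subgroup 2, the disjoint strata of ASCVD without heart failure and of neither condition.
- Add fewer than three comorbidities as the complement of subgroup 3.
- Report the estimate and 95% CI in every stratum.
- Prespecify treatment by heart failure (yes versus no) as the main contrast, with its 95% CI on the relative and the absolute scale. Naming one contrast matters, because three strata allow more than one.
- Exempt this contrast from the significance condition in section 11, so that it is reported whatever the overall p-value.
- State that a heart-failure-specific effect will be claimed only from this contrast, not from significance within a subgroup.

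The cost is SAP wording and a few more estimates from the same matched data. All seven comorbidities are matching factors, so pairs stay intact in these strata provided matching on the listed categories is exact. The downside is the imprecision shown in step 5: the interval may be wide, and it should carry the interpretation in place of a p-value.
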